6.7 BASELINE, TIME WINDOWS AND CALCULATED VISITS

For serum creatinine and values based on upon this measurement such as eGFR, baseline will be defined as the mean of all available measurements from the screening visit until start of randomised trial medication. For all other endpoints, baseline will be defined as the last available measurement before start of randomised trial medication.

Since the protocol specifies, that all measurements are taken at visit 2 before any intake of trial medication, all measurements at the first day of drug intake are assumed to qualify as baseline assessments.

For randomised patients without any treatment intake: For serum creatinine and values based on upon this measurement such as eGFR, baseline will be defined as the mean of all available measurements from the screening visit until and including the day of randomisation. For all other endpoints, baseline will be defined as the last available measurement before or on the day of randomisation.

Measurements taken after the first intake of randomised trial medication will be considered on-treatment values if they have been obtained up to end of the parameter specific follow-up period as defined in [Table 6.7: 1](#) below and will be assigned to the randomised study drug for efficacy and safety analyses.

Measurements taken after the end of the endpoint specific follow-up period after the last intake of study drug will be considered post-treatment values.

On-treatment (for OC-OT analysis) or all post-randomisation (for OC-AD analysis) efficacy and safety measurements will be assigned to visits based on time windows around the planned visit dates. These time windows are defined based on the planned number of days after the date of first administration of study drug.

The time window for the first visit after randomisation starts on the day after the first intake of study drug. The midpoint between two on-treatment visits defines the end of a time window, with the midpoint being included in the time window of the preceding visit.

Table 6.7: 1 Time windows for post-baseline efficacy measurements scheduled for each on-treatment visit for the first 3 years

Visit number	Visit label	Planned days	Time window (actual days after baseline)	
			Start	End
Endpoints assessed at each on-site visit (e.g. creatinine / eGFR)				
2	Baseline ^A	1	NA	1
3	Week 4	29	2	57
4	Week 12	85	58	155
6	Week 32	225	156	295
8	Week 52	365	296	449
10	Week 76	533	450	617
12	Week 100	701	618	785
14	Week 124	869	786	953
16	Week 148	1037	954	1121
18	...			
FU	FU	Trt stop + 30 days	Trt stop + 23 days	Trt stop + 45 days
KCCQ				
2	Baseline ^A	1	NA	1
4	Week 12	85	2	154
6	Week 32	225	155	295
8	Week 52	365	296	435
EOT	EOT / Post week 52	NA	436	Trt stop
FU	FU	Trt stop + 30 days	Trt stop + 23 days	Trt stop + 45 days

^A Only values taken prior to the start of treatment with randomised study drug can be considered baseline values. Time windows will be used for assignment of measurements to scheduled visits.

For examinations that are not planned at every on-treatment visit, the time windows will be defined according to the same algorithm, based on the midpoint between the planned visit day of such an examination. Examples for eGFR and KCCQ can be found in [Table 6.7: 1](#)

Only one observation per time window will be selected for analysis at an on-treatment visit – the non-missing value will be selected which is closest to the protocol planned visit day. If there are two observations which have the same difference in days to the planned day or if there are two observations on the same day, the first value will be used.

Baseline definition for concomitant therapies

Concomitant medication taken at baseline is any medication with start date ‘continued’ or before date of first study medication intake (randomisation date will be used for patients not treated) and end date continued on or after date of first study medication intake (randomisation date will be used for patients not treated).

Time windows for assignment of planned off-treatment measurement

For evaluation of the off-treatment assessment ‘at 30 day follow-up’ only values obtained at ≥ 23 days to ≤ 45 days after last trial drug stop will be considered.

The value that is closest to the planned day of 30 days after last trial drug stop will be used. If there are 2 values equally close, the later value will be used.

6.8 CALCULATION OF TIME TO EVENT

This section describes the calculation of the time to event and the time that patients without an event are in the study (under risk).

Consistent with that approach, the respective time intervals determine the start and end for the derivation of occurrence of a specific event.

For those patients with an event, the time to event is calculated as:

$$\langle \text{date of event} \rangle - \langle \text{start date} \rangle + 1$$

For those patients without an event, the time at risk is calculated as:

$$\langle \text{date of censoring} \rangle - \langle \text{start date} \rangle + 1$$

6.8.1 Start date

In general, the time to event will be derived from the date of randomisation.

If study drug administration happened before calling IVRS, the date of first drug administration will be used as start date.

For the following endpoints (analysed as occurrence or time to first event), the date of first drug intake will be used as start date:

- AE analyses according to [Section 7.8.1](#)
- Endpoints purely based on laboratory measurements, that include a relation to baseline (such as change decrease from baseline $\geq 40\%$, doubling vs baseline, etc.)

Please note, that for composite endpoints, that include component(s) using randomisation date and other component(s) using first drug intake date as start date, the time at risk for the composite will start with date of randomisation (which may be earlier). For the individual components, the component specific start date will be used.

6.8.2 Date of event

For adjudicated events, the date determined by the adjudication committee will be used; this can be different from the investigator reported date.

For the endpoints of time to CV death, time to all-cause mortality and time to non CV death the respective death date will be used rather than time to the first onset of the fatal AE.

For composite outcomes, e.g. time to adjudicated HHF or adjudicated CV death, the earliest onset date of the corresponding components will be used. For the component of CV death or other death components, date of death will always be used rather than the onset date also for composite outcomes.

For endpoints, where myocardial infarction (MI) and stroke are included as a fatal and non-fatal component, the onset of the event is considered for the derivation of time to first occurrence, not the date of death. For time to CV death the date of death is used for a fatal MI or fatal stroke.

The time to first occurrence type of endpoints based on laboratory data including endpoints including the requirement a “sustained” measurement are determined by the date of the first measurement that fulfils this condition.

For events with multiple possible episodes, such as HHF or all-cause hospitalisation, the onset date of the first episode will be used unless noted otherwise. The same applies to time-to-AE analysis.

For efficacy endpoint analyses (endpoints described in sections [7.4-7.6](#)):

As described in [Section 4](#), the follow-up period will not be included in the time at risk for efficacy endpoints. Therefore events later than the date of treatment discontinuation (if reason for discontinuation was completion) will not be counted.

For the primary endpoint and the key secondary endpoint of recurrent HHF, additionally there will be sensitivity analysis including all events up to individual trial completion including the FU period.

6.8.3 Censoring

The underlying principle is that the censoring date should be the last date a patient was known to be free of an endpoint event (e.g. free of each component of HHF + CV death).

For all endpoints except all-cause mortality and cause-specific death, patients without occurrence of a specific endpoint (composite endpoint or individual components) will be considered censored at the individual day of trial completion.

The individual day of trial completion will be the latest of:

- the last date the patient could be followed up for all non-fatal events as documented in the eCRF
- last onset of an AE or date of death
- onset dates of adjudicated events
- end of treatment
- last visit date (NYHA class, EQ-5D, KCCQ, pregnancy test, vital signs, ECG, or central laboratory- reported)

Censoring is considered independent from study drug intake.

All-cause mortality

A patient, without the event will be censored at the latest of

- Individual day of trial completion (without the restrictions defined above for patients with withdrawn consent or lost to follow-up)
- Last date known alive from the vital status page

Endpoints of any cause-specific death, e.g. CV death

The same censoring rule as in all-cause mortality applies, and in addition, date of death if died from other causes than the one specified in the endpoint.

Endpoints based on laboratory data only

Patients who already fulfil the respective condition at baseline are not considered in the number of patients at risk for this endpoint.

If a baseline laboratory measurement is not available for the parameter of interest, it is assumed that the patient did not experience the condition corresponding to the endpoint at baseline and the patient is included in the patients at risk for this endpoint. Patients without an event and available post-baseline laboratory measurements will be considered censored at the date of last laboratory sampling of the corresponding parameter. Patients with missing baseline laboratory required to derive a change from baseline and patients without laboratory data following the baseline measurement will be censored on the date of randomisation.

Composite endpoints

Only patients that are included in the analyses for all components of the composite endpoint will be included in the analysis of the composite.

Of those, a patient with at least one event in any of the components of the composite will be considered to have an event and the date of the first event will be used for the composite

endpoint. A patient without an event will be considered censored at the earliest of all censoring dates of the component endpoints.

For efficacy endpoint analyses (endpoints described in [Section 7.4-7.6](#)):

As described in [Section 4](#), for patients that completed the treatment phase as planned (primary reason for end of treatment being completion of treatment period according to protocol) the follow-up period will not be included in the time at risk for efficacy endpoints. Therefore for those patients, the minimum of the treatment discontinuation date and the above described dates will be used for censoring, except if specifically noted otherwise (for the sensitivity analysis). For patients that did not complete the treatment phase, the dates defined above will be used.

For the primary endpoint and the key secondary endpoint of recurrent HHF, additionally there will be a sensitivity analysis considering all events up to individual trial completion including the FU period.

Censoring for analyses up to trt stop + x days

For any analyses until a certain number of x days after treatment discontinuation (e.g. sensitivity analyses until 30 days after treatment discontinuation), censoring time will be the minimum of the censoring time as described above and treatment discontinuation + x days. Patients with an event after treatment discontinuation + x days will be censored at treatment discontinuation + x days.

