7.5.2 Other Secondary endpoints

Other secondary endpoints are exploratory. No correction for multiple hypotheses testing will be made.

- *Composite renal endpoint: Time to first event of chronic dialysis or renal transplant or sustained* reduction of $\geq 40\%$ eGFR (CKD-EPI)_{cr} or*
 - *(for patients with eGFR (CKD-EPI)_{cr} ≥ 30 mL/min/1.73 m² at baseline): sustained eGFR < 15 mL/min/1.73m²*
 - *(for patients with eGFR (CKD-EPI)_{cr} < 30 mL/min/1.73 m² at baseline): sustained eGFR < 10 mL/min/1.73 m²*

*An eGFR (CDK-EPI)_{cr} reduction is considered sustained, if it is determined by two or more consecutive post-baseline central laboratory measurements separated by at least 30 days (first to last of the consecutive eGFR values). If there is no additional measurement ≥ 30 days after the eGFR reduction is observed and the patient dies within 60 days of this measurement, then the eGFR reduction is also considered sustained.

Chronic dialysis is regarded as chronic if the frequency of dialysis is twice or more per week for at least 90 days.

- *Time to first adjudicated HHF*
- *Time to adjudicated CV death*
- *Time to all-cause mortality*
- *Time to onset of DM in patients with baseline pre-DM*

All time-to-event endpoints will be reported in days.

The same model and data frame as used in the primary analysis of primary endpoint will be applied to all these time-to-event endpoints. If the endpoint does not include any cause of death, a CIF plot with all-cause mortality as competing risk will be displayed; otherwise, a CIF plot with causes of death not included in the endpoint as competing risk will be displayed. For all-cause mortality a Kaplan-Meier plot will be displayed.

For time to first HHF and time to CV death, the analysis will be repeated based on investigator defined events. In addition, the analysis of time to CV death will be repeated to include all events up to 7 days prior a reported SARS-CoV-2 infection (based on broad scope SARS-CoV-2 infections)

- *Change from baseline in clinical summary score (HF symptoms and physical limitations domains) of the Kansas City cardiomyopathy Questionnaire (KCCQ) at week 52*

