7.6 FURTHER ENDPOINTS

Time to event endpoints

Further time to event endpoints will generally be analysed in a Cox proportional hazards model similar to the primary analysis on RS. If the endpoint does not include any cause of death, a CIF plot with all-cause mortality as competing risk will be displayed; otherwise, a CIF plot with causes of death not included in the endpoint as competing risk will be displayed.

If there are less than 14 patients with events, then only descriptive statistics will be presented.

Further time to event endpoints are the following:

- Time from first to second adjudicated HHF
- Time to first all-cause hospitalisation
- Time to new onset of atrial fibrillation
- Time to adjudicated MI (fatal or non-fatal)
- Time to adjudicated stroke (fatal or non-fatal)
- Time to adjudicated TIA
- Time to first event of all-cause mortality or all cause hospitalisation
- Time to first event of adjudicated CV death or adjudicated non-fatal MI
- Time to first event of adjudicated CV death or adjudicated non-fatal stroke
- Time to first event of adjudicated CV death, adjudicated non-fatal MI or adjudicated non-fatal stroke (3-point MACE)
- Time to progression to macro albuminuria (defined as UACR >300 mg/g) from baseline for patients with baseline UACR ≤ 300 mg/g
- Time to first new onset of sustained normo- or micro albuminuria (UACR ≤ 300 mg/g) in patients with macro albuminuria at baseline
- Time to first new onset of sustained normo albuminuria (UACR < 30 mg/g) in patients with micro- or macro albuminuria at baseline
- Time to first event of composite renal endpoint¹ or adjudicated CV death
- Time to first event of composite renal endpoint¹, adjudicated CV death or adjudicated HHF
- Time to first event of composite renal endpoint¹ or all-cause mortality

- Time to first acute kidney injury (based on the preferred term)
- Time to non-cardiovascular (non-CV) death (death cases not included in the definition of adjudicated CV death)
- Time to first investigator defined CV hospitalization

¹Composite renal endpoint defined as: *chronic dialysis or renal transplant or sustained* reduction of $\geq 40\%$ eGFR (CKD-EPI)_{cr} or*

- *(for patients with eGFR (CKD-EPI)_{cr} ≥ 30 mL/min/1.73 m² at baseline): sustained eGFR < 15 mL/min/1.73m²*
- *(for patients with eGFR (CKD-EPI)_{cr} < 30 mL/min/1.73 m² at baseline): sustained eGFR < 10 mL/min/1.73 m²*

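### The SAP censors laboratory-only endpoints at the last sample with no exception for death, so read literally the planned CIF plots cannot show mortality as a competing risk

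*SAP*

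**What the plan says.** All references are to the revised SAP (February 2021).

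- **Laboratory-only endpoints (Section 6.8.3).** "Patients without an event and available post-baseline laboratory measurements will be considered censored at the date of last laboratory sampling of the corresponding parameter". Also, "patients without laboratory data following the baseline measurement will be censored on the date of randomisation". Death is not mentioned in either rule.
- **Composite endpoints (Section 6.8.3).** "A patient without an event will be considered censored at the earliest of all censoring dates of the component endpoints".
- **Other rules in the same section do name death.** The list that defines the individual day of trial completion, used for endpoints in general, includes "last onset of an AE or date of death". The rule for cause-specific death adds, "in addition, date of death if died from other causes than the one specified in the endpoint".
- **Displays (Section 7.5.2, repeated in Section 7.6).** "If the endpoint does not include any cause of death, a CIF plot with all-cause mortality as competing risk will be displayed". For endpoints that include some deaths, the causes of death not included are the competing risk.

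The laboratory-only endpoints that can be identified from the SAP are in Section 7.6: "Time to progression to macro albuminuria", and the two endpoints of new sustained normo- or microalbuminuria. The main affected composite is in Section 7.5.2: "Composite renal endpoint: Time to first event of chronic dialysis or renal transplant or sustained" reduction in eGFR or a sustained low eGFR. The Section 7.6 composites that combine this renal endpoint with CV death, or with CV death and HHF, are built the same way.

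**The concern.** A CIF with death as competing risk needs the patient to be in the risk set on the day of death. The laboratory rule removes the patient at the last sample, which normally comes earlier. In the on-site schedule of Table 6.7: 1, later visits are 168 days (24 weeks) apart, for example day 365 to day 533, so the gap between last sample and death can be several months. If the rule is programmed as written, the death is lost as a competing event. The figure would be labelled as allowing for mortality but would estimate the incidence that would be seen if nobody died.

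At stake is the absolute incidence shown for a named secondary endpoint and for the albuminuria endpoints, in a heart failure population where death is not rare. Last-sample censoring is not itself the problem. It is a usual choice for the cause-specific Cox model of an endpoint that can only be detected at a visit. It does not fit the CIF.

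**Working it through.** **Step 1. Set the rules side by side.** Take a patient with samples up to day 533, no event, and death on day 600.

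| Rule | Result for this patient |
|---|---|
| Laboratory-only censoring (6.8.3) | Censored on day 533 |
| Composite with a laboratory component (6.8.3) | Earliest component date, so day 533 at the latest |
| General rule (6.8.3) | List of dates includes the date of death, day 600 |
| CIF display (7.5.2, 7.6) | Death is to be a competing event; no date rule is given |

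On day 600 the patient is no longer at risk under the first two rows, so the fourth row cannot be carried out.

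**Step 2. What the estimator then returns.** The Aalen-Johansen CIF sums S(t-) × d1(t)/n(t) over event times, where S is the probability of being free of both event and competing event. If no competing events enter, S is the Kaplan-Meier curve for the event alone and the sum equals 1 minus Kaplan-Meier exactly.

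**Step 3. How many deaths still enter.** The literal rule was simulated with sampling on days 29, 85, 225, 365, 533, 701, 869 and 1037 (Table 6.7: 1) and an extrapolated day 1205. Follow-up was 20 to 38 months (Section 9.6: 18 months accrual plus 20 months follow-up), with 20,000 patients per scenario. Assumed event rates were 3, 6 and 12% per year and assumed death rates 3, 6 and 10% per year. Between 7 and 42 of about 1,270 to 4,180 event-free deaths per scenario (about 0.5-1.4%) could still count, because they fell on a sampling day or before any post-baseline sample. In all nine scenarios the literal CIF matched 1 minus Kaplan-Meier to within 0.0003. With 6% for both rates, at the end of follow-up, the literal CIF was 0.1533, 1 minus Kaplan-Meier 0.1535, and the CIF with deaths counted 0.1394.

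**Step 4. Size at 2.5 years.** The SAP states no figure to reproduce and gives no event or death rates, so all rates here are assumptions. With constant event rate a and death rate b:

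- 1 minus Kaplan-Meier = 1 − exp(−2.5a)
- CIF = a/(a+b) × [1 − exp(−2.5(a+b))]

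| Endpoint type | a, b per year | 1 − KM | CIF | Difference (points) |
|---|---|---|---|---|
| Renal, low | 0.015, 0.04 | 0.0368 | 0.0350 | 0.18 |
| Renal, high | 0.03, 0.08 | 0.0723 | 0.0656 | 0.67 |
| Albuminuria, low | 0.15, 0.04 | 0.3127 | 0.2985 | 1.42 |
| Albuminuria, high | 0.25, 0.08 | 0.4647 | 0.4256 | 3.92 |

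Simulating the visit schedule with an added end-of-treatment sample gives slightly larger gaps: about 0.2 to 0.8 points for the renal type and about 1.7 to 4.7 for the albuminuria type. Sampling UACR at every on-site visit is a further assumption, since Table 6.7: 1 names only creatinine/eGFR as its example.

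**Step 5. Effect on the comparison of arms.** Take an event hazard ratio of 0.8, mortality of 6% per year in both arms, and the same formulas.

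- Control event rate 3% per year: the between-arm difference is 1.40 points (1 − KM) against 1.30 points (CIF), and the ratio of incidences is 0.806 in both.
- Control event rate 20% per year: the difference is 6.38 against 6.00 points, and the ratio is 0.838 against 0.837.

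So the absolute levels move, the difference between arms moves by 0.1 to 0.4 points, and the ratio barely changes.

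**The case against.** The strongest reply is that a programmer would not read the rules this way. Sections 7.5.2 and 7.6 explicitly ask for death as competing risk, and a curve without deaths would not meet that instruction. In Section 7.4.2 the SAP itself describes non-CV death as a competing event that counts as censoring for the primary endpoint, whose CIF is planned in Section 7.4.1. Being called censored in Section 6.8.3 therefore need not bar a death from entering a CIF. On this reading Section 6.8.3 fixes the date for patients with no event of any kind, and death is coded separately for the plot.

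That is sensible, but it is stated nowhere. The general and cause-specific rules name the date of death and the laboratory rule does not. A programmer is left with three options: censor at the last sample, place a competing event at the last sample, or place it at the date of death. What stands is that the contradiction depends on a literal reading, and that someone following the intent of the display sections could avoid it.

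Three stronger inferences are not supported:

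- **Onset of diabetes.** A reader might add this endpoint. The SAP does not define its components and refers to the protocol. If onset can also be established from reports or treatment, it is not a laboratory-only endpoint. It is affected only if its definition is laboratory-only.
- **Subgroups.** A reader might fear distorted subgroup incidences. Footnote 2 of Table 6.4: 1 plans the efficacy subgroups for the primary endpoint, CV death, first HHF, HHF (first and recurrent) and renal slope, none of which falls under this rule.
- **Treatment effect.** A reader might infer bias in the treatment comparison. The Cox hazard ratios are unaffected, and with equal mortality the ratio of incidences hardly moves (step 5).

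**Conclusion.** The point holds as a conflict between two stated rules. Applied literally, the censoring rule for laboratory-only endpoints, carried into composites by the earliest-date rule, turns the planned CIF into essentially 1 minus Kaplan-Meier and overstates cumulative incidence. The conflict comes from the text alone; its size rests entirely on assumed constant rates: deaths at 4-8% per year, renal-type events at 1.5-3% and albuminuria-type events at 15-25%. Under these, closed form and simulation together give about 0.2-0.8 and 1.4-4.7 points at 2.5 years.

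The scope is narrow: the albuminuria endpoints, the renal composite, and other composites with a laboratory component that leave some cause of death outside the endpoint. Section 7.5.2 calls the other secondary endpoints exploratory, and the albuminuria endpoints are further endpoints. No hazard ratio or confirmatory test changes, and the primary, HHF and CV-death displays are not touched. Severity: minor.

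**What to change.** Add to Section 6.8.3 a sentence such as: For CIF displays of laboratory-only endpoints, and of composites with a laboratory component, a patient who dies within the time at risk without the event, from a cause not included in the endpoint, enters as a competing event at the date of death; event-free survivors are censored as defined above, and censoring for the Cox model is unchanged.

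The cost is one extra status code in the time-to-event dataset, using death dates already collected. The displayed incidences become slightly lower. If the definition of diabetes onset turns out to be laboratory-only, the same sentence covers it.

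### In composites with a laboratory component, SAP 6.8.3 counts clinical events after the last sample but drops the matching event-free time

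*SAP*

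**What the plan says.** All references are to the revised SAP (last revision 12 February 2021).

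Under the composite rule in 6.8.3, "a patient with at least one event in any of the components of the composite will be considered to have an event", dated at the first such event. No limit is set at another component's censoring date. For everyone else the rule is: "A patient without an event will be considered censored at the earliest of all censoring dates of the component endpoints".

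The same section fixes the censoring date of a laboratory component. Patients with post-baseline samples and no event are "considered censored at the date of last laboratory sampling of the corresponding parameter". Those lacking a baseline value needed for the change, and "patients without laboratory data following the baseline measurement will be censored on the date of randomisation".

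Section 6.8.3 also has a general sentence. For all endpoints other than all-cause and cause-specific death, and expressly for composites as well as single components, patients without the event "will be considered censored at the individual day of trial completion". That does not agree with the composite rule.

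Three further endpoints in 7.6 begin "Time to first event of composite renal endpoint". They add CV death, CV death or HHF, and all-cause mortality respectively. The renal composite itself (7.5.2) combines sustained eGFR decline with chronic dialysis and renal transplant.

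**The concern.** The two halves of the composite rule use different observation windows. Take two patients, both last sampled at month 12 and both followed clinically to month 30. One has an HHF at month 24 and contributes 24 months and an event. The other has no event and contributes 12 months. From month 12 onward only the patient who will have the event remains in the risk set, so length of observation depends on outcome. A patient with no post-baseline sample adds either an event with its full time, or almost no time at all.

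Two consequences follow. Incidence rates are too high in both arms. And if laboratory attendance falls off faster in one arm, that arm's hazard is inflated more and the hazard ratio moves in a direction set by visit attendance.

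Elsewhere the plan does this correctly. For analyses up to treatment stop plus x days, 6.8.3 censors later events at the same date as event-free time. Only the composite rule lacks that second half.

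**Working it through.** **Inputs from SAP 9.6.** 10% yearly placebo event rate, HR 0.80, 18 months accrual plus 20 months follow-up (individual follow-up 20 to 38 months), 841 events, 4126 patients initially and about 5750 later.

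**Reproducing the plan's figure.** Placebo hazard λ = −ln(0.90) = 0.1054; active 0.80 × 0.1054 = 0.0843. Averaged over 20 to 38 months, the event probabilities are 0.2240 and 0.1837, mean 0.20387. Then 841 / 0.20387 = 4125.3, which rounds up to 4126. So the yearly rate is a yearly risk, and it is used that way below. The SAP gives no figure for the renal composites and no rate for stopping laboratory sampling. Its drop-out figure (below 1% per year) concerns leaving the trial.

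**Step 1: rates, all events clinical.** Assume follow-up C = 29 months = 2.417 years (midpoint of 20 and 38), and sampling that stops at rate s per year, independently of events.

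- Events per patient: 1 − exp(−λC) = 1 − 0.7752 = 0.2248
- Full time at risk: 0.2248 / 0.10536 = 2.134 years, i.e. 10.54 per 100 patient-years
- Time dropped by the composite rule: exp(−λC) × [C − (1 − exp(−sC))/s]

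For s = 0.05: 0.7752 × (2.4167 − 2.2764) = 0.109. The time left is 2.025 years, and the rate is 0.2248 / 2.025 = 11.10 per 100 patient-years.

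| Sampling stops, per year | Time dropped | Time kept | Rate per 100 patient-years | Inflation |
|---|---|---|---|---|
| 1% | 0.022 | 2.111 | 10.65 | +1.1% |
| 2% | 0.045 | 2.089 | 10.76 | +2.1% |
| 5% | 0.109 | 2.025 | 11.10 | +5.4% |
| 9% | 0.190 | 1.944 | 11.56 | +9.8% |
| 12% | 0.247 | 1.886 | 11.92 | +13.1% |

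**Step 2: ratio of rates when treatment does nothing** (active over placebo). 2% placebo versus 1% active: 10.65 / 10.76 = 0.990. 12% versus 9%: 11.56 / 11.92 = 0.970. Equal stopping gives 1.

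**Step 3: Cox model by simulation.** 5750 patients, 1:1 allocation (assumed), follow-up 20 to 38 months, independent stopping of sampling. With 5750 × 0.224 = 1288 events, the standard error of one log hazard ratio is 2/√1288 = 0.056. Over 400 replicates it is about 0.003, so estimates carry roughly ±0.006.

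- Clinical events only, 12% versus 9%: null HR 0.963 to 0.967, rejection about 10% to 11% at nominal 5%; a true 0.80 is estimated as 0.772.
- 2% versus 1%, 20% of events from the laboratory: null HR 0.99.
- Reversed direction, 5% placebo versus 10% active, 20% laboratory events, hazard 0.10 per year: null HR 1.042.
- Cutting events and time together at the last sample returned a null HR of about 1.00 throughout.

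**Step 4: laboratory share of events** (assumed), 12% versus 9%, true HR 1.

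| Laboratory share | Rule in 6.8.3 | Everyone followed to end of clinical follow-up |
|---|---|---|
| 20% | about 0.97 | about 1.005 |
| 40% | about 0.975 to 0.98 | about 1.013 to 1.016 |
| 90% | about 0.99 to 1.00 | about 1.03 to 1.04 |

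The 90% row stands in for the renal composite of 7.5.2, assuming few dialysis or transplant events. The last column is biased because eGFR status after the last sample is unobserved but treated as event-free.

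**The case against.** Most of the case on the other side stands, and it limits the point without removing it.

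- **Completers.** For patients who complete treatment as planned, 6.8.2 excludes later efficacy events and 6.8.3 censors no later than treatment stop. Where such a patient also has the follow-up sample 23 to 45 days after stop, the gap is zero. The problem falls mainly on patients who stop sampling but stay in clinical follow-up. That group is possible: 6.6.1 commits to following patients who stop treatment, and 6.3 notes that telephone visits may yield no measurements.
- **Status of the endpoints.** The renal composite is an exploratory other secondary endpoint (7.5.2), and the other three are further endpoints (7.6). None is in the testing hierarchy of 7.4.1.
- **Unknown rate.** Every stopping rate above is an assumption. At 1% per year in both arms the effect is negligible.
- **Stated principle.** Under 6.8.3, "the censoring date should be the last date a patient was known to be free of an endpoint event", which supports the last sample as the censoring date. It does not support counting events beyond that date.
- **Another reading.** A programmer could follow the general sentence and censor at trial completion. The composite sentence is more specific and probably governs, but the text should not leave this open.

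A reader might infer that the reported renal hazard ratios will be biased, or that type I error in the trial is inflated. The documents support neither: bias needs unequal stopping, for which there is no evidence here, and these tests carry no alpha.

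**Conclusion.** The rule is wrong as written, and the point is minor. It ties length of observation to outcome in the three composites of 7.6 that add death or HHF. The renal composite of 7.5.2 is touched only slightly, through dialysis and transplant.

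If sampling ends before clinical follow-up, rates are inflated in both arms, by about 5% at an assumed 5% per year. The hazard ratio moves only when stopping differs by arm: from about 0.99 (2% versus 1%) to about 0.96 (12% versus 9%) under the null when events are mostly clinical. It moves the other way if the active arm stops sooner, and less as the laboratory share rises. These sizes rest on constant hazards, stopping independent of events, and assumed stopping rates and laboratory shares.

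A reader might also conclude that following everyone to the end of clinical follow-up is the clean remedy. It is not, once laboratory events make up a real share of the composite. The primary endpoint has no laboratory component, so 841 events, the hierarchy and alpha stand.

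**What to change.** Add to 6.8.3: for composites with a laboratory component, only events up to the composite's censoring date (the earliest component censoring date) are counted, and patients whose first event falls later are censored at that date. This matches the existing rule for treatment stop plus x days.

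In the same edit, reconcile the general sentence that censors composites at the individual day of trial completion, so that one date applies to each composite.

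Follow-up of the clinical components to the end of clinical follow-up can be shown as a sensitivity analysis, with a note that eGFR status after the last sample is treated as event-free.

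The cost is one or two sentences and a change to the derivation program, with no new data. The downside is that a few clinical events after the last sample drop out of these exploratory analyses.
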